APPENDIX D

Collection and Storage of Tracheal Aspirates

Material

- Sterile catheter for endoscopy
- Special double walled tubes for microbiology 50 mL (type, company, city, country) with screw caps for storage and transport of infectious specimens
- Labels to be printed by Quintiles

Collection of tracheal aspirates

1. Several tracheal aspirates will be performed daily as often as medically indicated to ensure reasonable ventilation, using the routine, standardized procedure of the ICU and maintaining as aseptic conditions as possible during aspiration, collection and transfer of aspirate specimens to the labeled storage tube
2. Apply 100% O₂ bagging just before suctioning for collecting tracheal aspirates through the tracheal tube
3. **For aspirate 1 and 2, avoid whenever possible to dilute samples and no not use saline prior to collection to facilitate suction of viscous material**
4. For other aspirates, inject appropriate amount of saline into the tube to facilitate suction as per study site routine. As much as possible this amount should be kept stable for a given patient throughout the study and the precise volume recorded in the CRF
5. Insert the catheter at full-length and withdraw slowly with suction applied intermittently according to routine at ICU
6. Collect the tracheal aspirates in the prelabelled tube(s)
7. Estimate total volume and record in the CRF
8. For the 2 daily aspirates, the exact time should be recorded in the CRF
9. The first specimen of the day (e.g. Day 3, #1) will be collected by the ICU nurse after awaking, prior to administering azithromycin or placebo (0 hour specimen) and will be used for local bacteriology experiments (daily for isolation of *P. aeruginosa* strain, every third day for quantification as recommended in Study Schedule and in Sections 7.2.2 to 7.2.5) Strains will be stored at -70°C and shipped to Geneva for *in vitro* experiments
10. The second specimen of the day (e.g. Day 3, #2) will be collected daily by the ICU nurse early afternoon (ideally ~6 hours after infusion start), transferred to -70°C freezer at earlier possible time and will be shipped to Geneva for *in vivo* experiments performed in Geneva's laboratory as recommended in Study Schedule and in Sections 7.2.2 to 7.2.5 or stored as reserve samples
11. The total number of aspiration procedures per day and total volume thus collected will be recorded in the CRF as well as saline volume if appropriate

Specifications for tube labels

1. Labels for isolated strains (from Aspirate #1) or for tracheal aspirates (from Aspirate #2) will contain the following information: ANB 006 #2001, subject allocation number No, study day (Day 1 to 21), matrix (*P. aeruginosa*; trach asp. sample number (1, 2), sampling time, and date
2. One label will be attached to the internal tube (#1, 2), and one to the external tube(#1, 2)

APPENDIX D

Collection and Storage of Tracheal Aspirates (cont'd)

Storage

1. For specimens #1, store at 5°C (41 °F) and transmit daily to local laboratory (see Study Schedule and Section 7.2.) for strain isolation and quantification (usually every 3rd day)
2. Deep freeze at -70°C isolated *P. aeruginosa* strains on skim milk and glycerol obtained from Aspirate 1
3. Deep freeze specimens #2 (Geneva experiments) at -70 °C as quickly as possible, pending shipment in batches as agreed with study monitor. The parameters measured are listed under Study Schedule and Section 7.3.

APPENDIX E

Collection and Assessment of Bronchial Alveolar Lavage (BAL),

Bronchotracheal Aspirate or Protected Brush Specimen (PBS) on Day x

Material

- Sterile fibroscope tip or sterile protected specimen brush
- Sterile catheter
- Sterile saline (0.9 % sodium chloride)
- Special double walled tubes for microbiology 200 mL of adequate size, with screw caps for storage and transport of infectious specimens
- Labels to be printed by Quintiles

Collection of BAL (or bronchotracheal aspirate or PBS)

1. Depending on clinic setup, ICU routine, and patient condition, 3 different techniques may be used on the presumed Day x for confirming diagnosis of pneumonia:
 - Bronchoalveolar lavage (BAL)
 - Bronchotracheal aspirate
 - Protected brush specimen (PBS)
2. A BAL specimen will be taken only if there is strong suspicion of pneumonia to confirm diagnosis (Day x). This procedure should be performed by a trained intense care physician, only if medically not contraindicated, under aseptic conditions and operating as fast as possible to minimize the period when the patient is weaned off from mechanical ventilation. The procedure must be completed fast, using the routine, standardized procedure of the ICU and maintaining as aseptic conditions as possible during aspiration, collection and transfer of BAL specimens to the labeled storage tubes
3. Apply 100% O₂ bagging technique just before shifting the fibroscope or the brush through the tracheal tube
4. The fibroscope tip or brush will be positioned in a segmental ostium (lingual or right middle lobe), the selected side depending on the opacities seen on the lung radiography
5. In case of BAL, 2 aliquots of 50 mL of tepid saline will be infused through the aspiration port and collected via the same port by suction to collect the BAL fluid in 2 sterile tubes:
 - 1 tube will be sent to local laboratory for CFU analysis for diagnostic purposes, centrifugation, and differential cytology
 - 1 tube will be stored at -70 °C pending shipment to Geneva for special analysis (see Section 7.2.3)
6. If the protected brush technique is used, the brush will be disengaged from its sheath when *in situ*, gently sweeping the bronchial wall upon withdrawing. This specimen will be kept for local laboratory assessment. No specimen for the Geneva laboratory will be available using this technique
7. The patient will be put immediately back onto the mechanical ventilation as soon as the procedure is completed

APPENDIX E

Collection and Assessment of Bronchial Alveolar Lavage (BAL),

Bronchiotracheal Aspirate or Protected Brush Specimen (PBS) on Day x (cont'd)

Specifications for tube labels

1. Labels for tracheal aspirates will contain the following information: ANB 006 #2001, subject allocation number No, study day (Day x), matrix (BAL, brush, bronchial aspirate), sampling time, and date
2. One label will be attached to the internal tube and one to the external tube if appropriate (shipment to Geneva)

APPENDIX F

Recovery and Storage of Endotracheal Device

Material

- Sterile endotracheal tube, with T- tube and cuff
- Sterile bag
- Large container for microbiology of adequate size, with screw caps for storage and transport of infectious specimens
- Labels to be printed by Quintiles

Recovery of endotracheal device

1. On Day n –1 (i.e. on day of extubation or of exitus, but usually not if Day 20 unless ventilation may actually be discontinued in that given patient after 20 days of treatment), carefully remove the complete endotracheal device as aseptically as possible
2. Transfer into an appropriate sterile bag which will be sealed and freeze at –70°C as soon as possible
3. Pack into an appropriate container with screw lid when required for transport
4. In the event 2 endotracheal tubes have been used for a given patient (i.e. if the first extubation was not successful and the patient had to be re-intubated within 24 hours), one or two endotracheal tubes may be collected and transferred to Geneva laboratory

Specifications for tube labels

1. Labels for tracheal tubes will contain the following information: ANB 006 #2001, subject allocation number No, study day (Day n-1), tracheal tube, recovery time time, and date
2. One label will be attached to the sterile bag and one to the container as appropriate (shipment to Geneva)

APPENDIX G

Transport of Biological Specimens & Endotracheal Device

The packing will be the responsibility of the site monitor or delegate. Shipments will be organized in each centre in batches with specimens from 4 to 8 patients, using dedicated card boxes for each patient and matrix, with samples organized in a chronological order as per attached grid on box lid

- Do not allow any specimen samples to thaw at any time during the shipping preparation process
- Pack daily *P. aeruginosa* strains (obtained from Aspirate #1) and daily tracheal aspirate samples #2, BAL from Day x if available, and the intubation device collected on Day n-1 in chronological order, by patient, in large divided cardboard boxes to ensure protection against mechanical damage during shipment
- Seal carefully each cardboard box and record on each box study code, patient number and samples
- Include in the insulated container a photocopy of sample collection dates and time for each patient
- Place dry ice plates at bottom, sides and top of each insulated box, forming a house around the cardboard boxes containing the specimens and ensuring ~72 hours of deep freezing
- Close each insulated box with extra large tape and special plastic strings
- Apply on each insulated box the appropriate address and shipment labels (for dry ice, for bacteriological material etc.) as required for air freight
- Prepare the required proforma invoice and affix on each insulated box
- Ship the insulated boxes, preferably on Monday or Tuesday to:
[name] [name]
Département de Génétique et Microbiologie
Centre Médical Universitaire
[name]
[name]
Switzerland
Tel: [name]
Fax: [name]

To the attention of a laboratory technician to be specifically nominated

- Prior to each shipment and at least 3 days in advance forward a Fax message to the laboratory technician indicating the date of arrival in Geneva, flight, airway bill number, study number, study site, patient allocation numbers, amount of samples being shipped, number of boxes, a model of the proforma invoice, and a list of samples
- Obtain confirmation of availability by Fax and phone prior to shipment ensuring that the Geneva laboratory will be available to receive and store the samples on the projected delivery day
- Upon arrival in Geneva, the samples should be stored at -70°C , pending investigations listed in Section 7.2.2

APPENDIX H

Acute Physiology Chronic Health Evaluation (APACHE II)

Physiological Variable	High Abnormal Range					Low Abnormal Range			
	+4	+3	+2	+1	0	+1	+2	+3	+4
Temperature (rectal, °C)	 ≥41.0°	 39.0°-40.9°		 38.5°-38.9°	 36.0°-38.4°	 34.0-35.9°	 32.0°-33.9°	 30.0°-31.9°	 ≤29.9°
Mean blood pressure (mm Hg)	 ≥160	 130-159	 110-129		 70-109		 50-69		 ≤49
Heart rate (ventricular)	 ≥180	 140-179	 110-139		 70-109		 55-69	 40-54	 ≤39
Respiration rate (ventilated or not)	 ≥50	 35-49		 25-34	 12-24	 10-11	 6-9		 ≤5
Oxygenation: A-aDO ₂ or PaO ₂ (mm Hg)	 ≥500	 350-499	 200-349		 <200				
a. FI _{O2} ≥0.5 record A-aDO ₂									
b. FI _{O2} <0.5 record only PaO ₂					 PaO ₂ >70	 PaO ₂ 61-70		 PaO ₂ 55-60	 PaO ₂ <55
Arterial pH	 ≥7.7	 7.6-7.69		 7.5-7.59	 7.33-7.49		 7.25-7.32	 7.15-7.24	 <7.15
Serum sodium (mmol/L)	 ≥180	 160-179	 155-159	 150-154	 130-149		 120-129	 111-119	 ≤110
Serum potassium (mmol/L)	 ≥7.0	 6-6.9		 5.5-5.9	 3.5-5.4	 3-3.4	 2.5-2.9		 <2.5
Serum creatinine (µmol/L)	 ≥3.1	 1.8-3.0	 1.3-1.7		 0.5-1.2		 <0.5		
Acute renal failure: double score									
Hematocrit (%)	 ≥60		 50-59.9	 46-49.9	 30-45.9		 20-29.9		 <20
WBC (ths/mm ³)	 ≥40		 20-39.9	 15-19.9	 3-14.9		 1-2.9		 <1
Glasgow Coma Score (GCS) Score = 15 minus actual GCS									
A Acute Physiology Score (APS): Sum of 12 variables									
Serum HCO ₃ (venous mmol/L) Not preferred, only if no arterial pH	 ≥52	 41-51.9		 32-40.9	 22-31.9		 18-21.9	 15-17.9	 <15

APPENDIX H

Acute Physiology Chronic Health Evaluation (APACHE II) (cont'd)

B : Age Points						
B	Age (years)	≤44	45-54	55-64	65-74	≥75
	Assign Points	 0	 2	 3	 5	 6

C : Chronic Health Points		
C	If the patient has a history of severe organ system insufficiency or is immuno-compromised prior to hospital administration*	Assign Points
	a. For nonoperative or emergency postoperative patients	 5
	b. For elective postoperative patients	 2

*** Definitions**

Liver: Biopsy proven cirrhosis and documented portal hypertension; episodes of upper GI bleeding attributed to portal hypertension; prior episodes of hepatic failure/encephalopathy/coma

Cardiovascular: New York Heart Association Class IV

Respiratory: Chronic restrictive, obstructive or vascular disease resulting in severe exercise restriction; documented chronic hypoxia, hypercapnia, secondary polycythemia, severe pulmonary hypertension (>40 mm Hg) or respiratory dependency

Renal: Receiving chronic dialysis

Immuno-compromised: Drug-induced by recent and high dose steroid, chemotherapy, radiation, cyclosporine...
Disease-induced in leukemia, lymphoma, or AIDS

APACHE II		Score
APS Points	A	
Age Points	B	
Chronic Health Points	C	
Total APACHE II Score		
		Maximum possible score : 71
		Maximum clinical score: 55
		Range for selection: 10 to 25

APPENDIX I

Clinical Pulmonary Infection Score (CPIS)

This Clinical Pulmonary Infection Score (CPIS) has been originally developed by Pugin et al (1991), and later adapted by Singh et al (2000) to diagnose pneumonia on the basis of 7 parameters listed in the table below with the appropriate scoring system (for details on measurements, see Study Schedule on page 10 and Section 7.1.2):

Item	Units	Score 0	Score 1	Score 2
Body temperature	°C	≥36.5 and ≤38.4	≥38.5 and ≤38.9	≥39.0 or ≤36.0
Blood leukocytes	mm ³	≥4'000 and ≤11'000	<4'000 and >11'000	<4'000 and >11'000 and band forms ≥ 50%
Tracheal secretions		Absent	Present Non purulent	Present Purulent
Oxygenation Pa _{o2} /Fi _{o2}	mm Hg	>240 or ARDS*	--	≤240 and no ARDS*
Lung X-ray infiltrate		Absent	Diffuse or patchy	Localized
Progression of lung infiltrate		No progression	--	Progression (after CHF and ARDS excluded)
Tracheal aspirate culture (predominant pathogen)		None or rare or +	Moderate or heavy in culture	Same organism on Gram stain

ARDS = Acute respiratory distress syndrome

Defined as Pa_{o2}/Fi_{o2} ≤200, pulmonary wedge pressure ≤18, and acute pulmonary infiltrates

CHF = Congestive heart failure

Patients with a total CPIS for *Pseudomonas aeruginosa* of:

- <6 are unlikely to have pneumonia
- ≥6 have pneumonia
 - IF BAL ≥10⁴ CFU/mL and possible pneumonia if lower
 - OR if bronchotracheal lavage ≥10⁵ CFU/mL and possible pneumonia if lower
 - OR if protected specimen brush ≥10³ CFU/mL and possible pneumonia if lower

APPENDIX J

Electrocardiogram (ECG)

Recording

- Record 12-lead ECGs at a speed of 25 mm/sec using a validated electrocardiograph calibrated to 10 mm/mV (at least 5 complexes of good quality, 1 specimen at each time point as source document)
- Copies of original will be made for archiving purposes (1 set for investigator, 1 set for sponsor)
- Ensure that the subject has been supine for at least 10 minutes without disturbance such as aspiration prior to recording the ECG, avoiding event or activity known to prolong QT (falling asleep etc.)

Automated Analysis

- Cardiac frequency, PR interval, QT, QTc with Bazett's formula, QRS duration, possible U wave will be collected for safety purposes but will not be recorded in the CRF
- If QTc is prolonged (>450 msec) or if an artefact with the ECG machine reading is suspected, the QT will be measured manually by the investigator and QTc corrected with Bazett's formula

Assessment on Manual Parameters

- At study completion, transmit all ECGs for a given patient to an experienced cardiologist at each centre
- All ECG parameters will be measured manually by this cardiologist according to standard practice (HR, RR, QT)
- QT calculated for QTc (Bazett's) and wave morphology analysed for assessment at different time points vs. their respective pretreatment baseline (Δ)
- These data will be part of the CRF and of the Clinical Study Report
- Unless required at later stage, no centralized analysis is planned

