ED ₅₀	Effective dose at 50% of maximum pharmacological effect
ELF	Epithelial lining fluid
ERC	Ethical Review Committee
FI _{O2}	Percentage of inspired oxygen
Gamma-GT	Gamma glutamyltransferase (γ-GT)

Clinical Study Protocol ANB 006 #2001

GCP	Good Clinical Practice
GFR	Glomerular Filtration Rate
GI	Gastrointestinal
Hct	Hematocrit
HIV	Human Immunodeficiency Virus
HPLC	High Pressure Liquid Chromatography
HR	Heart Rate
i.v.	Intravenous
IC ₅₀	Inhibitory concentration eliciting 50% of maximum effect
ICH	International Committee for Harmonization
ICU	Intense Care Unit
MAC	Mycobacterium avium complex
MBP	Mean blood pressure (1/3 SBP + 2/3 DBP)
MCH	Mean corpuscular hemoglobin
MCHC	Mean corpuscular hemoglobin concentration
MCV	Mean corpuscular volume
MIC	Minimum inhibitory concentration
N	Number of observations
Pa _{O2}	Partial pressure of arterial oxygen
Pa _{O2} /FI _{O2}	Oxygenation
PBS	Protected brush specimen
PC	Predefined change
PD	Pharmacodynamics
PEEP	Positive end-expiratory pressure
PK	Pharmacokinetics
PT	Prothrombin time
QT	Duration between Q wave and T wave on the ECG (expressed in ms)
QTc	Corrected QT-interval (Bazett's formula) in ECG
RBC	Red blood cells
SAE	Serious adverse event
SBP	Systolic Blood Pressure
SD	Standard deviation
t _½	Elimination half-life in plasma
t _{max}	Time to reach maximal drug concentration in plasma
V	Volume of distribution
VAP	Ventilator associated pneumonia
WBC	White blood cells

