4.3 Exclusion Criteria

Subjects presenting with any of the following will not be included in the study:

- Poor prognosis as judged by Apache II score >25
- Pregnant females
- Grossly under- or overweight (BMI <18 or >29)
- Ongoing therapy with a macrolide (clarithromycin, erythromycin, azithromycin, telithromycin)
- Known allergy to any macrolides
- Proven *P. aeruginosa* pneumonia (with documented CFU>10⁴ in BAL or PBS)
- Ongoing antipseudomonal therapy with a susceptible colonizing strain as proven by antibiogramme*

* A list of recommended antibiotics deprived of antipseudomonal activity is provided in Section 6.2 to facilitate the choice of the investigators and to homogenize antibiotic treatment according to type of infections. For patients on antibiotherapy with activity against pseudomonas prior to study entry, they will be maintained in the screening phase for 48 hrs, pending results of antibiogramme on the colonized strain. If found to be susceptible to the antibiotic used, the patient will be excluded from the study; if found to be resistant, the patient will be included in the study (also see Section 6.2)

- Anticipated short duration of mechanical ventilation (≤ 3 days)
- Known drug interaction which could interfere enough with absorption, metabolism, or excretion and thus could decrease efficacy or raise safety concern despite plasma drug monitoring of concomitant therapy (for examples see Section 6.2)
- Severe hepatic insufficiency (type C i.e. score >10 on Child Pugh scale, Appendix A) [Pugh et al 1973]
- Sick sinus syndrome or known long QT syndrome or $QTc >500$ msec
- Recent donation of blood or participation in another clinical trial within 3 months (Europe) or 1 month (USA)
- Any situation exposing the patient to higher risk or possibly confounding results of the study

Any local or country specific regulations must be respected. Any waiver of the inclusion and exclusion criteria listed above must be approved by the investigator and by the monitor on a case-by-case basis prior to enrolling the subject. This must be documented by both the monitor and the investigator.

No subject will be allowed to enroll in this study more than once if study drug was administered. However a patient may be screened on a 2nd occasion under another screening number if he did not meet all inclusion and exclusion criteria in the first instance.

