6. PRIOR AND CONCOMITANT ILLNESSES AND TREATMENTS

6.1 Prior and Concomitant Illnesses

Since this study will be performed in severely ill patients requiring mechanical ventilation, concomitant illnesses, postsurgical complications, or multiple trauma are expected in this population and can be among others:

- Deterioration of underlying diseases such as congestive heart failure or pulmonary insufficiency
- Development of acute respiratory distress syndrome (ARDS) due to aspiration, inhalation of chemicals, overdose of narcotics, or sepsis
- Thoracic or multiple trauma
- Complications after visceral, cardiovascular, pulmonary surgery or post transplantation

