7.2.3 Study days

Day 1

On the morning of Day 1, prior to infusion of test drug, the following procedures will be performed:

- Adverse events
- Body temperature (tympanic or rectal) ~7:00
- Blood pressure, heart rate, respiration rate (~8:00)
- Blood (see Appendix B)
 - Hematological profile
 - Blood chemistry
 - WBC & CRP
- Specimen for blood culture (only if clinically indicated)
- Blood gases
- Oxygenation: $\text{Pa}_{\text{O}_2} / \text{FI}_{\text{O}_2}$
- CPIS (use X-ray of same day whenever possible, else of previous day)
- Clinical endpoints
- Tracheal aspirate 1 (transfer to local laboratory, for parameters see Section 7.1.2 above)
 - Quantification of *P. aeruginosa* (CFU/mL)
 - Isolation of *P. aeruginosa* strain (storage -70°C)

After these activities the test drug will be infused over 1 hour, usually from 8 to 9 o'clock.

Post treatment activities will include:

- ECG, 1 to 4 hours post infusion start
- Tracheal aspirate 2 (for freezing and transfer to Geneva laboratory for investigation, for parameters see Section 7.1.2 above), collected ~6 hours post infusion start
- Blood pressure, heart rate, respiration rate (~6 hours post infusion start)
- BAL if required medically (suspicion of pneumonia)

- Lung X-ray if required medically or if pneumonia (after Day x)
- Body temperature (tympanic or rectal) ~17:00
- Local tolerance (24 hours)
- Systemic tolerance (24 hours)

Day 2

On the morning of Day 2, prior to infusion of test drug, the following procedures will be performed:

- Systemic adverse events from previous night
- Local tolerance
- Body temperature (tympanic or rectal) ~7:00
- Blood pressure, heart rate, respiration rate (~8:00)
- Blood for WBC & CRP
- Specimen for blood culture (only if clinically indicated)
- Blood gases
- Oxygenation: Pa_{O2}/ FI_{O2}
- Clinical endpoints
- Tracheal aspirate 1 (transfer to local laboratory, for parameters see Section 7.1.2 above)
 - Isolation of *P. aeruginosa* strain (storage -70°C)

After these activities the test drug will be infused over 1 hour, usually from 8 to 9 o'clock.

Post treatment activities will include:

- Tracheal aspirate 2 (for freezing and transfer to Geneva laboratory for investigation, for parameters see Section 7.1.2 above), collected ~6 hours post infusion start
- Blood pressure, heart rate, respiration rate (~6 hours post infusion start)
- BAL if required medically (suspicion of pneumonia)
- Lung X-ray if required medically or if pneumonia (Day x)

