Twelve-lead ECG will be recorded as described in Appendix I, at a speed of 25 mm/sec and calibrated at 10 mm/mV. If a QTc is prolonged (>450 ms or >60 ms vs. baseline), manual checking of QT and calculation of QTc with Bazett's formula will be performed by the investigator for safety purposes. Manual reading will be performed at study completion by experienced cardiologist on study site. To perform centralized reading is not planned unless required at later stage.

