Adverse events reported during trial will be listed by treatment. Absolute and relative frequencies of subjects with adverse events (treatment emergent adverse events) will be tabulated by study part, by body system and by dose. Frequencies of subjects with severe and/or related adverse events will be summarized likewise. Local tolerance will be provided by time and by treatment and will be summarized with descriptive statistics for categorized variables by time and treatment.

Laboratory variables

Laboratory findings will be evaluated using a system of predefined changes and clinically significant abnormal values (provided by sponsor), taking into account the investigator's normal ranges. Listings of all variables will be provided by time and by treatment. Descriptive analysis will be presented by time and by treatment.

Physical examination

Listing of all variables will be provided by time and by treatment group. Descriptive analysis for raw data and for changes from baseline will be presented when appropriate.

Blood pressure and heart rate

Listing of all variables will be provided by time and by treatment. Descriptive analysis for raw data and for changes from baseline will be presented by time and by treatment.

ECG

Twelve-lead ECG will be recorded as described in Appendix I, at a speed of 25 mm/sec and calibrated at 10 mm/mV. If a QTc is prolonged (>450 ms or >60 ms vs. baseline), manual checking of QT and calculation of QTc with Bazett's formula will be performed by the investigator for safety purposes. When a patient will have completed treatment, all his ECGs will be transmitted to an experienced cardiologist for manual measurement as per Appendix J. The ECG parameters calculated manually by cardiologist will be used for statistical analysis.

Occurrence of infections

Information on distribution of infections to any bacterial strain will be collected and occurrence compared between study treatment.

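### Bazett is the only correction fixed for the analysed QTc, so within-patient changes and counts above 450 ms partly reflect heart rate; RR is already read, and a second correction is a minor, nearly free improvement

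*Protocol*

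**What the plan says.** The abbreviations list defines QTc once for the whole protocol: "Corrected QT-interval (Bazett's formula) in ECG". Section 7.3 uses the same correction for the bedside flag: "If a QTc is prolonged (>450 ms or >60 ms vs. baseline), manual checking of QT and calculation of QTc with Bazett's formula". Section 11.3 repeats that rule and adds: "The ECG parameters calculated manually by cardiologist will be used for statistical analysis".

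Appendix J describes those manual values: "All ECG parameters will be measured manually by this cardiologist according to standard practice (HR, RR, QT". The assessment itself is then "QT calculated for QTc (Bazett's) and wave morphology analysed for assessment at different time points vs. their respective pretreatment baseline". These data go into the CRF and the study report.

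On-treatment recordings are scheduled as "ECG, 1 to 4 hours post infusion start" on Day 1, Day 3, every third day after that and the last day. The only ECG scheduled before the first dose is the screening one (section 7.2.2), so it is the pretreatment baseline.

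The protocol treats QT as a recognised risk. Section 4.3 excludes patients with "Sick sinus syndrome or known long QT syndrome or" a QTc above 500 ms, and section 6.2 asks for care with QTc-prolonging co-medication. It names no other correction, heart-rate adjustment or sensitivity analysis for QTc.

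**The concern.** Bazett divides QT by the square root of RR. That removes heart rate only if QT really varies with RR to the power 0.5. If the relation is flatter, the corrected value still rises with heart rate, and a change in Bazett QTc mixes repolarisation with rate.

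The population makes this worth asking. Section 6.1 expects conditions such as "Development of acute respiratory distress syndrome (ARDS) due to aspiration, inhalation of chemicals, overdose of narcotics, or sepsis", as well as trauma, heart failure and surgical complications. Treatment lasts up to 20 days. The last ECG may fall on the day of extubation after improvement or on the day pneumonia is diagnosed. Heart rate may plausibly differ between baseline and those days, although the protocol gives no heart-rate data.

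What is at stake is how the QTc summaries are read: individual changes from baseline, the number of patients above 450 ms and, if heart rate differs by arm, the azithromycin-placebo difference.

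**Working it through.** The protocol gives no QTc effect size, power or error rate, so there is no planned figure to reproduce. The check is algebra on the stated correction.

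**Inputs.** From the protocol: the Bazett correction, the limits of 450 ms and 60 ms, and manual QT and RR on every ECG. Assumed: the true QT-RR exponent b (1/3, 0.40 or 0.50), the rate-independent QTc (Q) and all heart rates.

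**Formula.** If QT = Q × RR^b with RR = 60/HR, then Bazett QTc = QT / RR^0.5 = Q × (60/HR)^(b − 0.5).

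**1. Readings for a true Q of 400 ms**

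| HR (bpm) | b = 1/3 | b = 0.40 | b = 0.50 |
|---|---|---|---|
| 60 | 400.0 | 400.0 | 400 |
| 90 | 428.0 | 416.6 | 400 |
| 100 | 435.5 | 421.0 | 400 |
| 120 | 449.0 | 428.7 | 400 |

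**2. Within-patient change, no drug effect, HR 85 to 115.** +21.9 ms (b = 1/3), +12.7 ms (0.40), 0 ms (0.50).

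**3. Same heart-rate change in both arms.** Let HR fall from 110 to 85 and let the drug raise Q from 400 to 420 ms.
- b = 1/3: placebo reads 442.5 to 423.9 = −18.6 ms; azithromycin reads +2.6 ms; difference 2.6 − (−18.6) = +21.2 ms.
- b = 0.40: placebo −10.8 ms; azithromycin +9.9 ms; difference +20.7 ms.

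The single-arm change is badly distorted, but the arm difference recovers the true +20 ms almost exactly.

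**4. Different heart rate by arm, no QT effect, 100 versus 90 bpm.** 7.6 ms (b = 1/3), 4.4 ms (0.40), 0 ms (0.50), from unrounded values.

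**5. Crossing 450 ms on rate alone.** HR = 60 × (450/Q)^(1/(0.5 − b)). For Q = 410 ms this is about 105 bpm (b = 1/3) or 152 bpm (0.40). For Q = 420 ms it is about 91 or 120 bpm.

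**6. Simulation with no drug effect.** Two million draws per setting. Assumed: Q mean 410, SD 25 ms, within-patient correlation 0.7; mean HR 80, 95 or 105, SD 15 to 18, within-patient correlation 0.5.

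| Quantity | b = 1/3 | b = 0.40 | b = 0.50 (same as true Q) |
|---|---|---|---|
| Share above 450 ms | 24–49% | 14–27% | 5.5% |
| Share with change above 60 ms | 0.7–0.9% | 0.3% | 0.1% |
| SD of change (ms) | 24.5–25.4 | 21.5–22.0 | 19.4 |
| Correlation of QTc change with HR change | 0.53–0.56 | 0.35–0.38 | 0 |

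The count above 450 ms is the sensitive quantity. The count above 60 ms stays small in every setting.

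**7. Fridericia under the same model.** The reading is Q × (60/HR)^(b − 1/3). At 100 bpm with Q = 400 it is 400 ms (b = 1/3), 400 × 0.6^0.0667 = 386.6 ms (0.40) and 400 × 0.6^0.1667 = 367.4 ms (0.50). The errors of 0, −13 and −33 ms compare with Bazett's +36, +21 and 0 ms. On the exponent scale Fridericia is the closer of the two when b is below the midpoint (1/3 + 1/2)/2 = 0.417.

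**The case against.** A reader might infer that Bazett will hide a real azithromycin effect on QT, or create a false one, in this trial. The documents do not support that. The trial is randomised, double blind and placebo controlled, and safety data are presented by treatment. As step 3 shows, a heart-rate fall shared by both arms leaves the arm difference at about +21 ms for a true +20 ms. The +22 ms in step 2 would appear equally in both arms.

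The arm comparison needs a heart-rate difference by arm, and the documents do not supply a gap as large as 10 bpm. Section 11.5 expects about 10% pneumonia on placebo. Suppose pneumonia raises heart rate by 20 to 30 bpm (assumption) and azithromycin prevents every case. The mean gap is then 0.10 × 20 to 30 = 2 to 3 bpm. At 7.6/10 = 0.76 ms per bpm (b = 1/3), that is about 1.5 to 2.3 ms.

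Nor do the documents say that heart rate is high. In the APACHE II table of Appendix H a rate of 70–109 scores zero, so the entry range of 10–25 does not imply tachycardia. Appendix J asks for at least 10 minutes of undisturbed supine rest before recording. At an exponent of 0.50 there is no bias at all.

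Bazett is the only correction but not the only ECG quantity kept: HR, RR and QT also go into the CRF and the study report. Section 11.3 summarises heart rate by time and treatment, so an imbalance could be seen. It also promises a detailed statistical plan before decoding, which could add another correction.

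Most of this stands and limits the point. It does not remove it. The protocol fixes Bazett by name for the analysed QTc, and the within-patient changes and counts above 450 ms depend on heart rate whatever happens between arms.

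**Conclusion.** The point holds as a minor one. With Bazett alone, and a true QT-RR exponent below 0.5, individual QTc changes and counts above 450 ms partly reflect heart rate. At 100 bpm a true 400 ms reads about 36 ms too high (exponent 0.33), 21 ms (0.40) or not at all (0.50). Shifts common to both arms largely cancel. The between-arm bias is about 8, 4 or 0 ms for 100 versus 90 bpm and arises only if such a gap exists.

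The size rests on the assumed exponent and assumed heart rates; the protocol gives neither. A conclusion that the trial's QT comparison is unreliable in either direction would go too far. QTc is a secondary safety variable analysed descriptively, and the sample size and the primary test are untouched.

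**What to change.** In Appendix J and the ECG part of section 11.3:

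- Compute Fridericia QTc (QT / RR^(1/3)) from the same manually read QT and RR, and make it the main descriptive QTc scale by arm, including the change from the pretreatment ECG.
- Keep Bazett QTc as a supportive column. The protocol uses its limits with Bazett, so any count of Fridericia values against them should be labelled as descriptive and shown beside the Bazett count.
- Report QT change adjusted for RR change, alongside heart rate by arm at the same time points. This matters because Fridericia errs in the other direction if the exponent is well above one third (step 7), and the adjusted analysis does not depend on choosing either fixed exponent.

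Eligibility, the bedside flags and all clinical rules stay as written. The cost is one extra formula and table column, plus the RR-adjusted summary, all from data already collected.
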